4.3 Expected duration

The total duration of the study, from the first visit of the first patient to the preparation of the final report, is estimated to be 12 months.

The planned recruitment period is 7 months. Considering that the proposed sample is 180 patients, the total average recruitment rate during the study should be no less than 0.86 patients per day. Competitive recruitment will be carried out among authorized research centers.

The approximate duration of each patient in the study is up to 41 days.

5. Study population

5.1 Eligibility Criteria

5.1.1 Inclusion criteria

- Can voluntarily give their signed informed consent.
- Be able and willing to comply with scheduled visits, treatment plan, and other study procedures.
- Be of legal age.
- Women of childbearing potential must ensure continued use (initiated \geq 30 days prior to signing the CRF) of hormonal contraceptive method or IUD during the study period.
- Present a diagnosis of mild to moderate dry eye, defined by an OSDI rating \geq 13 and one of the following:
 - o Corneal staining with more than 5 sites.
 - o Conjunctival staining with more than 9 sites.
 - o Tear film breakdown time < 10 seconds.

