1.2 Synopsis

Title of the study:	
Phase IV non-inferiority clinical trial to compare the efficacy of Humylub Ofteno® PF ophthalmic solution against Hyabak® and Lagricel Ofteno® PF on the ocular surface of patients with mild to moderate dry eye syndrome	
Study number: SOPH087-0120/IV	Data created: 15-ene-20
Protocol version: 2.0	Date of version: 27-abr-20
Therapeutic indication: Ocular lubricant	Use: Dry eye
Estimated duration of the study (from the first visit of the first patient to the preparation of the final report): 12 months	Clinical development phase: IV
Objectives: Objective principal: 
 Demonstrate the non-inferiority of Humylub Ofteno® PF compared to Hyabak® and Lagricel Ofteno® PF in the efficacy of treating patients with dry eye, using the OSDI (ocular surface disease index) test score Secondary objectives: 
 Demonstrate the non-inferiority of Humylub Ofteno® PF compared to Hyabak® and Lagricel Ofteno® PF in the efficacy of treating patients with dry eye, through non-invasive measurement of tear breakup time (TBUT). Demonstrate the non-inferiority of Humylub Ofteno® PF compared to Hyabak® and Lagricel Ofteno® PF in the efficacy of treating patients with dry eye, through changes in corneal and conjunctival staining with fluorescein. Demonstrate the non-inferiority of Humylub Ofteno® PF compared to Hyabak® and Lagricel Ofteno® PF in the efficacy of treating patients with dry eye, based on changes in corneal and conjunctival staining with lysamine green. 	

 • Demonstrate the non-inferiority of Humylub Ofteno® PF compared to Hyabak® and Lagrel Ofteno® PF in the efficacy of treating patients with dry eye, based on changes in conjunctival hyperemia. • Demonstrate the non-inferiority of Humylub Ofteno® PF compared to Hyabak® and Lagrel Ofteno® PF in the safety of treating patients with dry eye, based on the incidence of chemosis. • Demonstrate the non-inferiority of Humylub Ofteno® PF compared to Hyabak® and Lagrel Ofteno® PF in the safety of treatment of patients with dry eye, based on the incidence of adverse events (AEs).
Hypotesis:
H_0 = The Humylub Ofteno® PF ophthalmic solution is not inferior in efficacy to its comparators after 30 days of treatment, showing a 35% decrease in the final OSDI test score from baseline in at least 30% of exposed patients.
$H_0: P_A - P_B \leq \delta$

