H_1 = The Humylub Ofteno® PF ophthalmic solution is inferior in efficacy to its comparators after 30 days of treatment, as it does not show a 35% decrease in the final OSDI test score from baseline in at least 30% of exposed patients.
$H_1: P_A - P_B > \delta$
Study design:
Phase IV non-inferiority, controlled, open-label, comparative, multicenter clinical trial.
Number of subjects (planned and analyzed):
Number of patients planned: 60 evaluable patients per arm. Total sample = 180 evaluable patients.
Diagnosis and main inclusion criteria:

 - Patients diagnosed with mild to moderate dry eye.
Selection criteria:
Inclusion criteria:

 - Can voluntarily give their signed informed consent. - Be able and willing to comply with scheduled visits, treatment plan, and other study procedures. - Be of legal age. - Women of childbearing potential must ensure the continuation (initiated ≥ 30 days prior to signing the informed consent form [ICF]) of the use of a hormonal contraceptive method or intrauterine device (IUD) during the study period. - Present a diagnosis of mild to moderate dry eye, defined by an OSDI rating ≥ 13 and one of the following: 
 o Corneal staining with more than 5 sites.

- Conjunctival staining with more than 9 sites.
- Tear film breaking time < 10 seconds.

Exclusion criteria:

[figure not shown]
- Women who are pregnant, breastfeeding, or planning to become pregnant within the study period.
- Have participated in another clinical research study ≤ 30 days prior to the screening visit.
- Have previously participated in this study.
- Have a CVAM of 20/200 or worse in one of the eyes.
- Present an ophthalmological diagnosis of:
 - Allergic, viral, or bacterial conjunctivitis.
 - Blefaritis anterior.
 - Parasitic infestations in any ocular structure or its appendages.
 - Unresolved eye trauma.
 - Healing diseases of the ocular surface.
 - Corneal or conjunctival ulcers.
 - Filamentous keratitis.
 - Neurotrophic keratitis.
 - Bullous keratopathy.
 - Neoplastic diseases on the ocular surface or adnexa.
 - Diseases with fibrovascular proliferations on the conjunctival and/or corneal surface.
 - Retinal and/or posterior segment diseases that require treatment or threaten visual prognosis.
 - Glaucoma.
 - Disorders of the eyelids that cause palpebral malpositions, limit the proper closing or opening of the eyelids, or are the cause of epiphora.

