2.7 Justification

The great impact that the diagnosis of SOS represents, both socially, economically and scientifically, has been established, without a doubt; but above all for the quality of life of patients who suffer from it. Epidemiological evidence describes that in some regions the incidence of this disease can reach up to more than 50% of the population. There are currently multiple therapeutic options for the management of SOS, among which ocular lubricants occupy a main place due to their effectiveness in reducing the symptoms associated with the condition and as an aid in the restoration of tear film homeostasis. In the search for the best formulation to manage this type of patient, the rheological properties of substances such as glycosaminoglycans, a family to which both active ingredients of Humylub Ofteno® PF belong, have been used. By combining HS and CS, it is possible to offer patients with SOS symptomatic relief, as well as improvement in signs and alterations related to the vicious circle that characterizes SOS.

Humylub Ofteno® PF is a product that is already marketed, and whose safety profile has already been previously studied; however, it was decided to carry out this study to compare its efficacy with two formulations containing sodium hyaluronate at different concentrations. The intention of this study is to confirm that patients with mild to moderate dry eye find an equal or greater decrease in their

symptoms with the use of Humylub Ofteno® PF, compared to reference products, and to continue in this way to expand the information available on this ophthalmic solution and strengthen its efficacy and safety profile.

3. Objectives and hypotheses

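### The entry rule defines mild to moderate dry eye as OSDI 13 or more with no upper limit, so patients in the protocol's own severe band (OSDI 33 or more) are eligible

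*Combined protocol and SAP*

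**What the plan says.** **Population label.** The title in the synopsis (section 1.2) places the trial "on the ocular surface of patients with mild to moderate dry eye syndrome". The synopsis gives the main diagnosis as "Patients diagnosed with mild to moderate dry eye". Section 2.7 states: "The intention of this study is to confirm that patients with mild to moderate dry eye find an equal or greater decrease in their" symptoms, compared with the reference products. Section 6.1.3.1 rests its dose rationale on the same severity label. Section 10.2.2 plans from an earlier study in mild to moderate dry eye.

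**Entry rule.** Section 5.1.1 reads "Present a diagnosis of mild to moderate dry eye, defined by an OSDI rating" of 13 or more, together with one of three signs:
- "Corneal staining with more than 5 sites"
- "Conjunctival staining with more than 9 sites"
- "Tear film breakdown time < 10 seconds"

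The synopsis carries the same rule, so this is not a slip in one place.

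**Severity bands.** Section 7.4.4.2 scores OSDI from 0 to 100 and sets mild at 13 to 22, moderate at 23 to 32 and severe at 33 or more.

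**Objectives and hypotheses.** Sections 3.1 and 3.2 speak of patients with dry eye, without a severity grade. The hypotheses in 3.3 name no severity.

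**The concern.** The criterion names a bounded severity range and then defines it by a floor alone. The three signs are also one-sided, with no limit at the severe end. Followed literally, the rule enrols patients whom section 7.4.4.2 calls severe and counts them as mild to moderate.

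What is at stake is which population the result describes. A non-inferiority finding from patients scoring anywhere from 13 to 100 would be reported under a mild to moderate label. Section 7.3 mentions no stratification by severity and section 10 plans no severity subgroup, so the reader of the final report would not see the mix. The mix can also affect the response rate, because the hypotheses count patients with a 35% fall in OSDI, and that fall is a different number of points at different baselines.

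**Working it through.** No figure in the plan has to be reproduced here. The check sets the rule against the bands, looks for a cap elsewhere, and then asks how large the severe share could be.

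**1. Rule against bands.** Eligible OSDI range (5.1.1): 13 to 100. Mild and moderate together (7.4.4.2): 13 to 32. Severe: 33 to 100. A patient with OSDI 60 and break-up time 5 seconds meets both parts of the rule and falls in the severe band.

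With all 12 items answered, the score is (item sum) × 25/12. Of the 42 attainable scores at or above 13, 9 lie below 33 (14.6 to 31.25) and 33 lie at or above it (33.3 to 100). These are counts of scale values and say nothing about how many patients hold them.

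**2. Search for a cap in the exclusions (5.1.2 and synopsis).**

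| Exclusion | Can remove advanced disease? | Limits OSDI? |
|---|---|---|
| Management requiring all stage 2 TFOS DEWS II treatments | Yes | No |
| Corneal or conjunctival ulcers | Yes | No |
| Filamentous or neurotrophic keratitis | Yes | No |
| Acuity of 20/200 or worse in one eye | Possibly | No |
| Other condition, at the investigator's judgment | Possibly | No |

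**3. Possible severe share.** The documents give no baseline OSDI mean or SD, so all means and SDs below are assumptions. For normal scores truncated at 13, the share is

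P(X ≥ 33) / P(X ≥ 13) = [1 − Φ((33 − μ)/σ)] / [1 − Φ((13 − μ)/σ)].

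| Assumed μ, σ (before truncation) | Calculation | Share at 33 or more |
|---|---|---|
| 20, 8 | 0.052 / 0.809 | 6% |
| 22, 8 | 0.085 / 0.870 | 10% |
| 25, 12 | 0.252 / 0.841 | 30% |
| 30, 15 | 0.421 / 0.872 | 48% |
| 35, 15 | 0.553 / 0.929 | 60% |
| 40, 12 | 0.720 / 0.988 | 73% |

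The model ignores the exclusions in step 2, which could lower any of these figures.

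**4. What a 35% fall means across the range.** 0.35 × 13 = 4.6 points; 0.35 × 33 = 11.6 points; 0.35 × 60 = 21 points. In item steps with 12 answers, an item sum of 7 (OSDI 14.6) needs 0.35 × 7 = 2.45, so 3 steps. An item sum of 29 (OSDI 60.4) needs 0.35 × 29 = 10.15, so 11 steps.

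**The case against.** **The words mild to moderate act as the cap.** An investigator who reads 5.1.1 with 7.4.4.2 in hand might decline a patient at OSDI 60. That is possible, so enrolment of severe patients is not certain. But the criterion goes on to define the words by the floor and one sign, and that definition admits the patient. Sites could apply the rule differently, which is itself a reason to settle it.

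**OSDI grades symptoms, and entry also needs a sign.** Section 7.4.4.2 does introduce the bands as symptom severity. However, section 2.1 presents OSDI as a means of grading the condition, the variable table in 7.4.4 describes it in the same way, and 5.1.1 uses it to define the population.

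**Randomisation protects the comparison.** This stands. Severe patients are not steered to one arm, and a percentage response already scales with baseline. A reader might infer that the missing cap biases the comparison; nothing in the documents supports that. Nor would a cap alter the stated sample size, since the formula in 10.2.2 does not use baseline severity.

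**Other stronger readings.** Three are tempting and do not hold:
- That severe patients will be a large share. This depends on the assumed mean; the lower rows in the working give 6% to 10%.
- That the stage 2 exclusion is the only brake on advanced disease. The ulcer, keratitis and acuity exclusions also act.
- That the objectives must be reworded. They carry no severity grade.

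**Conclusion.** The point holds as a contradiction within the protocol. The inclusion rule calls mild to moderate a range that runs through the whole of the protocol's own severe band, and no exclusion caps OSDI. This follows from sections 5.1.1, 5.1.2 and 7.4.4.2 and needs no assumption.

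The size is unknown. From about 6% to about 73% of eligible patients could score 33 or more, and both ends rest on assumed normal scores with assumed means and SDs. The harm is to the description and generalisability of the result; the validity of the randomised comparison is not affected. The sponsor should correct it.

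**What to change.** Reconcile the entry rule (5.1.1 and synopsis), the bands (7.4.4.2) and the population label. Which cut-off is right is for the sponsor. There are two routes:

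1. **Align entry with the label.** Give 5.1.1 and the synopsis an upper OSDI limit that matches the protocol's own moderate band. State how scores between 32 and 33 are treated: with 10 items answered, an item sum of 13 gives 13 × 25/10 = 32.5, which falls between the printed bands. Cost: possibly slower recruitment.

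2. **Align the label with entry.** Keep entry open and describe the population as OSDI 13 or more in the title, synopsis, justification (2.7) and the eventual conclusion. Add one table of the primary result by the 7.4.4.2 bands. With 60 patients per arm over three bands, cells would average 60/3 = 20 per arm, so the table can only be descriptive and should be labelled so. Cost: wording and one table.

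On either route the severity statement in 6.1.3.1 must agree with the final entry rule; this implies nothing about the regimen. The objectives in section 3 can stay as they are.

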5.1.2 Exclusion Criteria

- Women who are pregnant, breastfeeding, or planning to become pregnant within the study period.
- Have participated in another clinical research study \leq 30 days prior to the screening visit.
- Have previously participated in this study.
- Have a CVAM of 20/200 or worse in one of the eyes.
- Present an ophthalmological diagnosis of:
 - o Allergic, viral, or bacterial conjunctivitis.
 - o Anterior blepharitis.
 - o Parasitic infestations in any ocular structure or its appendages.
 - o Unresolved eye trauma.
 - o Healing diseases of the ocular surface.
 - o Corneal or conjunctival ulcers.
 - o Filamentous keratitis.
 - o Neurotrophic keratitis.
 - o Bullous keratopathy.
 - o Neoplastic diseases on the ocular surface or adnexa.
 - o Diseases with fibrovascular proliferations on the conjunctival and/or corneal surface.

- Retinal and/or posterior segment diseases that require treatment or threaten visual prognosis.
- Glaucoma.
- Disorders of the eyelids that cause palpebral malpositions, limit the proper closing or opening of the eyelids, or are the cause of epiphora.
- Have a management of your dry eye that requires the implementation of all stage 2 treatments of the TFO DEWS II treatment and stage management recommendations for dry eye disease.
- Have a history of drug addiction or drug dependence current or within the last two years prior to signing the FCI.
- Have a history of eye surgical procedure within the last 3 months prior to signing the FCI.
- Be a soft or hard contact lens wearer. You will be able to enter in case of suspending its use during the study, you must comply with 15 days without using the contact lens prior to your inclusion.
- Have another medical condition, acute or chronic, that in the investigator's judgment may increase the risk associated with participation in the study or administration of the investigational product, or that may interfere with the interpretation of the results of the study.
- Have known hypersensitivity to the components of the investigational products.

5.2 Patient Removal and Replacement Criteria

- Withdrawal of the letter from the FCI.
- Presentation of serious AEs related or not to the investigational product, which at the discretion of the PI and/or sponsor could affect the patient's ability to continue with study procedures safely.
- Non-tolerability or hypersensitivity to any of the compounds used during the tests (fluorescein, lysmine green, tetracaine).
- Non-tolerability or hypersensitivity to any of the investigational drugs.

5.3 Lifestyle Considerations

For the study, participants may need to modify some lifestyle activities to comply with the following:

- Abstain from tobacco use.
- Refrain from using electronic vaporizers.

- Avoid submerging yourself in water without eye protection (*goggles*).
- Avoid direct exposure to fans (including air conditioning vents) during activities that involve vision. 24 hours before your check-up visits.
- Maintain your sleep-wake cycle with which you enter the study.

5.4 Counting failures

A screening failure is defined as those participants who agree to participate in the study, giving their consent, but who are not assigned to a treatment group, i.e., do not enter the study. It is necessary to report at least the following information on counting failures:

- Demographics.
- Details of the failure to count (specify whether it is due to eligibility criteria, which one, or some other reason for the failure).
- Presence of serious AEs during the count.

This is necessary to comply with the CONSORT (Consolidated Standards of Reporting Trials) guidelines for the publication of results or to respond to possible questions from regulatory authorities.

Patients who do not meet the eligibility criteria to participate in the study due to a specific modifiable factor may re-participate in the scrutiny. Patients in this case must use the same initial count number.

5.5 Recruitment and Retention Strategies

This is a phase IV study, which is planned to be conducted at several research centers. The selected centers will be responsible for the recruitment of patients.

The minimum expected recruitment rate is 0.93 patients per business day. Because this study will be carried out in patients with mild to moderate SOS, a very common condition in the usual ophthalmological consultation, the participation of at least three research centers will be required.

The duration of the patient's participation in the study is approximately 41 days, during which time they will only have to attend three visits after the screening, however, the screening and baseline appointments can be made on the same day, so no retention problems are anticipated. However, patients will be entitled to travel support for transportation and to comply with their visits. Other strategies to improve patient retention include, but are not limited to:

- Clearly inform the importance of the study and the benefits that the population will obtain from its results.
- Make calls or send text messages to remind you of appointments or activities to do.
- Provide a printed calendar and an identification card to remember appointments and activities that will be carried out, in addition to the estimated duration of the same.
- Offer flexible hours of operation.
- Systematic organization of the study procedures, so that the patient does not last longer than necessary in his visit.
- Minimize patient wait times.

All materials to be delivered to the patient or recruitment strategies implemented by the Centers will be submitted for approval by the corresponding committees.

5.6 Procedure in case of loss of follow-up

For this protocol, loss of follow-up is defined as those patients who were randomized, who at some points were active patients in the study, but their final evaluation could not be completed.

If the participating patient does not attend their appointment, the research center must make a call to find out the reason and will attempt to make a new appointment within the established window period or an unscheduled appointment. In case it is not possible to make an appointment, the presence of AEs and the reason for leaving the study will be asked, as minimum data.

A follow-up loss of <20% is considered not to be a problem for the validity of the results obtained based on the sample size calculations. See point 10.2 Calculation of the sample size.

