7.4 Outcome variables

7.4.1 Primary outcome variables

- OSDI score (TE: visits 1 and final).

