10.1.3 Procedure for handling missing data

The safety assessment will include in the analysis all those patients (both eyes) who have been exposed at least once to the intervention, regardless of the visit at which they were eliminated from the study (ITT).

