10.1.4 Deviations from the statistical analysis plan

According to the calculation of the sample size to meet the objective of the study, 50 evaluable patients are required per arm. If this number is not met due to a loss of patients greater than 20% contemplated in this protocol (loss of follow-up or withdrawal of ICF), the sponsor may replace these patients.

The results obtained from the replaced patients will continue to be used for safety analysis and will be part of the ITT.

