10.1.5 Patients included in the analysis

Those patients who meet an adherence $\geq 65\%$ of the expected weight of the PI and $\geq 80\%$ of expected applications in the patient's diary, will be included in the statistical analysis to meet the objective of the study. If it is not possible to assess the weight of the IP, only the patient's diary will be considered.

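### No day-31 OSDI is required after removal or a failed rebooking, and efficacy is analysed only in adherent patients, so the primary comparison has no all-randomised check

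*Combined protocol and SAP*

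**What the plan says.** All references are to the combined protocol and SAP.

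- **Outcome.** Section 7.4.1 gives the primary variable as "OSDI score (TE: visits 1 and final"). Section 3.3 defines response as a 35% fall in the final score from its initial value. Section 1.3 puts the final visit at day 31 ± 1 and schedules no early-exit visit.
- **Removal.** Section 5.2 lists consent withdrawal and "Non-tolerability or hypersensitivity to any of the investigational drugs", with the same rule for the test compounds. It also lists serious AEs that the investigator or sponsor judges could affect the patient's "ability to continue with study procedures safely". It asks for no assessment after removal.
- **Missed visits.** Section 5.6 requires a call and an attempt to rebook. If that fails, "the presence of AEs and the reason for leaving the study will be asked, as minimum data". A loss below 20% is "considered not to be a problem for the validity of the results obtained based on the sample size calculations".
- **Analysis sets.** Section 10.1.3, headed as the missing-data procedure, covers safety only: "The safety assessment will include in the analysis all those patients (both eyes) who have been exposed at least once to the intervention". Section 10.1.4 adds: "The results obtained from the replaced patients will continue to be used for safety analysis and will be part of the ITT". Section 10.1.5 states that patients with at least 65% adherence by bottle weight and 80% by diary "will be included in the statistical analysis to meet the objective of the study". No ITT efficacy analysis is specified.

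**The concern.** A patient without a day-31 score has no value for the response defined in 3.3. The plan does not say whether the visit-1 score, which will usually exist, stands in for it. Such patients drop out of the comparison, and so do patients below the adherence thresholds who do have a score. Both exclusions happen after randomisation.

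The trial is open-label (4.2) and OSDI is patient-reported, so leaving could depend on both product and symptoms. The protocol contains one route for this. Section 8.4.1 has lack of therapeutic response reported as a serious AE, 7.4.4.2 treats a 40% rise in OSDI as an AE for lack of efficacy, and serious AEs can lead to removal under 5.2. Nothing shows that this route will be used unequally across arms.

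If more non-responders are lost from Humylub, its completers look better and non-inferiority is easier to claim. If more are lost from a comparator, the bias runs the other way. If losses are unrelated to response, the completer comparison stays near its nominal error. The reassurance in 5.6 does not address this, because a sample-size allowance protects patient numbers and not the comparability of those who remain.

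**Working it through.** **1. What the 20% allowance does.** Section 10.2.2: 50 × 1.20 = 60 per arm. The allowance is a head count and uses no information on who is lost. (The 50 itself cannot be re-derived, because the comparator response rate is not stated; that is a separate matter and nothing below depends on it.)

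**2. Would collecting the score be enough?** Four drops a day for 30 days is 120 applications (6.1.3), and the 80% diary rule needs 96. A patient removed at visit 1 (day 17 ± 1) has had 15 to 17 full days:

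- 15 × 4 = 60, and 60/120 = 50%
- 17 × 4 = 68, and 68/120 = 57%

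This takes all 120 applications as the denominator, the natural reading of the formula in 6.4. The patient fails 10.1.5, so a day-31 score would be used only if an all-randomised analysis existed.

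**3. Possible size.** Taken from the plan: 60 per arm, a 10-point margin, α = 0.05 used one-sided as in the 10.2.2 formula, and 30% response on Humylub. Assumed: 40% response on one comparator, which places the truth at the margin, and every loss pattern. Non-inferiority is declared when

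(p̂_A − p̂_B) − 1.645 × √[p̂_A(1 − p̂_A)/n_A + p̂_B(1 − p̂_B)/n_B] > −0.10,

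and the probability is summed exactly over all pairs of binomial outcomes. With losses a (Humylub) and b (comparator), completers number 60 − a and 60 − b. Three loss mechanisms were used:

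- (1) Losses unrelated to response: completer rates stay at 30% and 40%.
- (2) Non-responders twice as likely to be lost: with r = (a/60)/[p + 2(1 − p)], the completer rate is p(1 − r)/(1 − a/60). For a = 11 and p = 0.30, r = 0.1833/1.70 = 0.108 and the rate is 0.30 × 0.892/0.817 = 32.8%. For 3 lost at p = 0.40 it is 40.8%.
- (3) Every lost patient is a non-responder.

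False non-inferiority among completers:

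| Losses, Humylub vs comparator | (1) | (2) | (3) |
|---|---|---|---|
| 0 vs 0 | 5.2% | 5.2% | 5.2% |
| 7 vs 7 | 5.3% | 4.9% | 4.3% |
| 8 vs 3 | 6.0% | 7.6% | 10.6% |
| 11 vs 3 | 4.9% | 7.8% | 13.8% |
| 3 vs 11 | 5.1% | 2.7% | 1.1% |
| 11 vs 11 | 5.4% | 4.6% | 3.8% |

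**4. How likely are such splits by chance?** With equal loss risk and 60 of 120 patients on Humylub (hypergeometric), 8 or more of 11 losses on Humylub has probability 10.2%, and 11 or more of 14 has 2.2%.

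**5. Would one non-response rule repair it?** False non-inferiority with losses unrelated to response:

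| Losses | Missing = non-response, both arms | Missing = non-response, Humylub only |
|---|---|---|
| 8 vs 3 | 2.8% | 1.7% |
| 11 vs 3 | 1.8% | 1.1% |
| 3 vs 11 | 16.4% | 3.8% |
| 11 vs 11 | 7.0% | 1.2% |

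The both-arms rule is not conservative for non-inferiority when the comparator loses more. The Humylub-only rule, with missing comparator scores left out, is usually strict but not a bound: at 3 vs 11 it reaches 7.4% if responders are twice as likely to be lost.

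**The case against.** **The effect is small in moderate scenarios.** This is true. Under mechanisms (1) and (2) the uneven splits give 2.7% to 7.8%, and with balanced losses error stays between 3.8% and 5.4% under all three. The double-digit figures need both an uneven split and every lost patient to be a non-responder.

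**Few losses are likely.** The products are marketed lubricants used for 30 days, section 5.5 plans travel support and reminders, and 5.6 makes the call mandatory. Test-compound reactions should cost little: both dyes are used at screening, and OSDI is listed before staining at later visits. Yet the plan itself allows for 20% loss.

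**A minimum does not forbid collecting OSDI.** Correct, and a rebooked appointment is taken here to repeat the missed visit. But optional collection varies by site, and 10.1.5 would still exclude most early leavers.

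**The calculation uses a responder test, while 7.4.4 lists ANOVA for OSDI.** The responder model follows 3.3 and 10.2.2. The percentages illustrate that comparison for one comparator; they do not measure error in the ANOVA, and adherence exclusions are not modelled.

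**Section 3.3 refers to exposed patients**, which could mean an all-exposed denominator. Section 10.1.5 points the other way, so the text does not settle it.

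**The sensitivity analyses are imperfect.** This stands. At 3 vs 11 the both-arms rule gives 16.4%, and 25.4% if responders are twice as likely to be lost. That is why no single rule is proposed.

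**Conclusion.** The concern holds. Followed as written, the plan requires no day-31 OSDI from removed patients or those whose visit is not rebooked, and it analyses efficacy only in adherent patients. The primary outcome then has no all-randomised check. The bias is conditional: it needs losses that relate to response and either differ in number between arms or relate to response differently in each arm. It can run in either direction.

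The magnitude is unknown. In the illustration, false non-inferiority moves from 5.2% to between 1.1% and 13.8%, the extremes requiring every lost patient to be a non-responder. All splits, the 40% comparator rate and the link to response are assumptions. The sponsor should make this change; confidence is medium, because the textual gap is clear but its practical effect depends on losses not yet seen.

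**What to change.** - **5.2 and 5.6:** separate stopping product from withdrawing consent. Every randomised patient who has not withdrawn consent completes OSDI at the day-31 time, in person or by phone, with mode and on/off-product status flagged. A patient who reacts to a test compound skips the dye tests and still gives OSDI. When to stop product remains a clinical decision.
- **5.6:** confine the statement on losses below 20% to sample size.
- **10.1.5:** add an all-randomised analysis of the primary outcome using every collected day-31 score whatever the adherence, reported beside the adherent set. Give the number missing per arm and state what role, if any, the visit-1 score has.
- **Missing day-31 scores:** two sensitivity analyses: (i) missing as non-response in both arms; (ii) missing as non-response in Humylub only, with missing comparator scores left out. Say in advance how disagreement between analyses will be read.

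The cost is wording in three sections, eCRF flags for mode and product status, and one table with two sensitivity rows. The call is already required. The downside is that off-product or phone scores may pull the arms together, which favours non-inferiority, so both analysis sets should be shown.
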